11. HEALTH OUTCOMES ANALYSES

Not applicable.

Confidential Page 27 of 40

12. INTERIM ANALYSIS

An interim analysis is planned and will be based on patients who complete or early term the study on or before 30 Apr 2024.

Confidential Page 28 of 40

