6.4.2 Study Stopping Criteria

This study will be regularly monitored for safety and tolerability based on routine review of safety data. On a quarterly basis during study conduct, all open-label safety data (adverse events, clinical

Protocol ITI-007-503 23 Aug 2021

laboratory measures, vital signs, ECGs, and C-SSRS) will be reviewed. If the Study Physician determines at any point during the open-label treatment period that the risk of study continuation outweighs the benefits, a determination to stop the study can occur in conjunction with discussions with the Head of Clinical Development or designee, the Head of Drug Safety and Pharmacovigilance, and the Chief Medical Officer.

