9.5 Interim Analysis

No interim analysis is planned for this study.

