2. INTRODUCTION

This statistical analysis plan (SAP) provides the technical and detailed elaboration of the statistical analyses of the efficacy and safety data as outlined and/or specified in the Protocol Amendment 1 (dated 23 Aug 2021) of Study ITI-007-503.

Study ITI-007-503 ("Study 503") is an international, open-label, multicenter, 6-month study to assess the safety and tolerability of lumateperone as adjunctive therapy in patients with MDD. The Study will be performed at approximately 120 study centers. No *de novo* patients will be enrolled.

Patients who have safely completed the lead-in studies may be eligible to participate in this Open-label Safety Study. Lead-in study completion is defined as a patient who completes the double-blind treatment period (ie, all scheduled visits up to and including Visit 8) of the lead-in study.

The study will be conducted as follows:

- A Screening Period of one day in duration. Potential patients rolling over from the lead-in studies will be evaluated for eligibility during the Screening/Baseline Visit (Visit 1/Day 1) which is the same visit as Visit 8/Day 43 of the lead-in study. Patients who meet all eligibility criteria at the Screening/Baseline Visit (Visit 1/Day 1) will be dispensed lumateperone 42 mg to be self-administered each evening without respect to food.
- A **26-week Open-label Treatment Period** during which patients will self-administer lumateperone, to be taken each evening, without respect to food. Background ADT should also continue as previously prescribed, with no change of dose from the lead-in studies. Patients will attend visits on Weeks 1, 2, 3, 4, 6, 8, 10, 12, 14, 16, 18, 20, 22, 24, and 26. The Open-label Treatment Period will last a total of 26 weeks. A patient will be defined as a treatment completer if the patient completes the Open-label Treatment Period (all scheduled visits up to and including Visit 16/Week 26).
- A 2-week Safety Follow-up Period. A Safety Follow-up visit will occur approximately 2 weeks after completion of the Open-label Treatment Period or after the Early Termination (ET) Visit. Any ongoing AEs at the Safety Follow-up Visit must be followed until resolution, until the AE stabilizes, until it is determined to be not clinically significant, or until the patient is lost to follow-up.

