Patients who prematurely discontinue should be seen for an ET visit as soon as possible and will also be asked to return to for a Safety Follow-up visit approximately 2 weeks after Visit 16/ET visit.

The maximum per-patient study duration for the Open-label Safety Study will be approximately 28 weeks.

The Schedule of Evaluations is presented in Table 2-1. Detailed descriptions of the procedures conducted at each study visit are provided in Section 8.5 of the Protocol.

Confidential Page 7 of 40

Table 2-1: Schedule of Evaluations

Study Period	Screening /Baseline Visit ¹											Safety Follow Up					
Visit Number	1	2	3	4	5	6	7	8	9	10	11	12	13	14	15	16/ET	
Study Day	1	8	15	22	29	43	57	71	85	99	113	127	141	155	169	183	197
Study Week	0	1 (+/-3 days)	2 (+/-3 days)	3 (+/-3 days)	4 (+/-3 days)	6 (+/3 days)	8 (+/-3 days)	10 (+/-3 days)	12 (+/-3 days)	14 (+/-3 days)	16 (+/-3 days)	18 (+/-3 days)	20 (+/-3 days)	22 (+/-3 days)	24 (+/-3 days)	26 (+/-3 days)	28 (+/-3 days)
Informed consent	X																
Inclusion/Exclusion criteria	X																
Physical examination	X															X	
Vital signs ³	X	X	X	X	X	X	X	X	X	X	X	X	X	X	X	X	X
12-lead ECG ⁴	X	X					X				X					X	
Clinical laboratory assessments (hematology, serum chemistry, urinalysis) ⁵	X	X					X				X					Х	
Urine drug testing ⁶	X	X					X				X					X	
Serum/urine pregnancy test ⁷	X	X			X		X		X		X		X		X	X	
MADRS	X	X	X	X	X		X		X		X		X		X	X	X
CGI-S	X	X	X	X	X		X		X		X		X		X	X	
AIMS/BARS/SAS	X	X			X		X		X		X		X		X	X	
C-SSRS	X	X	X	X	X	X	X	X	X	X	X	X	X	X	X	X	X
PK sampling		X8					X ⁹										
AEs/SAEs	X	X	X	X	X	X	X	X	X	X	X	X	X	X	X	X	X
Concomitant medications	X	X	X	X	X	X	X	X	X	X	X	X	X	X	X	X	X
ADT prescription dispensation ¹⁰	X																
ADT compliance check	X	X	X	X	X	X	X	X	X	X	X	X	X	X	X	X	

Confidential Page 8 of 40

Study Period	Screening /Baseline Visit ¹										Safety Follow Up						
Visit Number	1	2	3	4	5	6	7	8	9	10	11	12	13	14	15	16/ET	17
Study Day	1	8	15	22	29	43	57	71	85	99	113	127	141	155	169	183	197
Study Week	0	1 (+/-3 days)	2 (+/-3 days)	3 (+/-3 days)	4 (+/-3 days)	6 (+/3 days)	8 (+/-3 days)	10 (+/-3 days)	12 (+/-3 days)	14 (+/-3 days)	16 (+/-3 days)	18 (+/-3 days)	20 (+/-3 days)	22 (+/-3 days)	24 (+/-3 days)	26 (+/-3 days)	28 (+/-3 days)
Lumateperone dispensation	X	X	X	X	X	X	X	X	X	X	X	X	X	X	X		
Lumateperone return and compliance check		X	X	X	X	X	X	X	X	X	X	X	X	X	X	X	

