4.2 Safety Population

Safety Population includes all patients in the Enrolled Population who receive at least one dose of open-label lumateperone.

Confidential Page 12 of 40

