5. SUBJECT DISPOSITION

The number of patients in each study population will be summarized by study center as follows:

- The number of patients who were screened will be summarized overall by study center.
- The number of patients in the Safety Population will be summarized overall.

In addition, the number and percentage of patients who complete the Open-label Treatment Period and who prematurely discontinued from the Open-label Treatment Period will be summarized overall and by reasons for premature discontinuation for the Safety Population.

Confidential Page 13 of 40

6. **PROTOCOL DEVIATIONS**

Major protocol deviations for the study will be defined as in the Protocol Deviation Management Plan for the Study. The number and percentage of patients with major protocol deviations during the Open-label Treatment Period will be provided overall for the Safety Population.

Confidential Page 14 of 40

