16. CHANGES TO ANALYSES SPECIFIED IN PROTOCOL

No major changes made to the analyses specified in the latest protocol amendment for Study ITI-007-503 Amendment 1 (dated 23 Aug 2021).

Confidential Page 38 of 40

17. REFERENCES

None.

Confidential Page 39 of 40

18. APPENDICES

None.

Confidential Page 40 of 40

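### SAP 12 plans an interim analysis that protocol 9.5 rules out, on a set that recently dosed patients can enter only by dropping out

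*SAP*

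**What the plan says.** Protocol 9.5 is a single sentence: "No interim analysis is planned for this study". SAP 12 is also a single sentence and says the opposite: "An interim analysis is planned and will be based on patients who complete or early term the study on or before 30 Apr 2024". SAP 16 reports "No major changes made to the analyses specified in the latest protocol amendment", naming Amendment 1 of 23 Aug 2021, and does not mention the interim. SAP 2 names the same amendment as the text the SAP elaborates, so these are current passages in conflict, not a difference from superseded text.

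The tables the interim might draw on are defined for a different set. SAP 4.2: "Safety Population includes all patients in the Enrolled Population who receive at least one dose of open-label lumateperone". SAP 5 tabulates completers and those "who prematurely discontinued from the Open-label Treatment Period will be summarized overall and by reasons for premature discontinuation for the Safety Population". SAP 10 runs all safety analyses on that same population.

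On what completion means, SAP 2 says "A patient will be defined as a treatment completer if the patient completes the Open-label Treatment Period", that is, through Visit 16 at Week 26. It also says "The maximum per-patient study duration for the Open-label Safety Study will be approximately 28 weeks". SAP 12 uses neither term: it speaks of completing the study.

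**The concern.** Part of this is a conflict of text. The protocol excludes an interim, the SAP schedules one, and the section meant to list departures from the protocol is silent.

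The larger issue is who is counted. Membership depends on having finished, one way or the other, by a calendar date. Patients dosed long enough ago are all in, whatever their outcome. Patients dosed recently cannot have completed, so they are in only if they have already stopped. The rule therefore selects on the outcome that SAP 5 reports. Safety and tolerability are the primary objective, so discontinuation and AE withdrawal are central outputs. Interim and final rates could differ because of the selection rule alone, and a reader of the interim could take that difference for a finding about the drug.

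**Working it through.** **Dates.** In the schedule of evaluations Visit 16 is Day 183 and Visit 17 is Day 197. Counting back from 30 Apr 2024, Day 183 is reached by the cut-off only if Day 1 was on or before 31 Oct 2023 (28 Oct to 3 Nov with the ±3-day window). If completion means Visit 17, the date is 17 Oct 2023. A patient dosed later can enter only by terminating early.

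**Inputs.** From the documents: about 760 patients, 26 weeks of treatment, 28 weeks in all. The plan states no interim size, accrual dates or drop-out rate, so there is no figure of its own to reproduce. Assumed: uniform accrual over A = 52, 78, 104 or 130 weeks, ending g = 0, 13 or 28 weeks before the cut-off; constant drop-out hazard; true 26-week discontinuation p = 20%, 30% or 40%.

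**Formula.** Let u be weeks from first dose to cut-off, uniform on (g, g + A), let h = −ln(1 − p)/26, and let C = 26 or 28 be the week at which a patient counts as complete. Then

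interim rate = D / (D + (1 − p)·P(u ≥ C)), with D = E[1 − exp(−h·min(u, 26))].

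**One case by hand (p = 30%, A = 104, g = 0, C = 26).**
- Dosed within 26 weeks of the cut-off: 26/104 = 25%, or 190 of 760. The other 570 contribute 0.30 × 570 = 171 discontinuations.
- Mean probability that a recent patient has already stopped: 1 − 0.30/(−ln 0.70) = 1 − 0.30/0.3567 = 0.159. This gives 190 × 0.159 ≈ 30 early terminations.
- About 160 patients still on treatment are left out.
- Interim rate = (171 + 30)/(570 + 30) = 201/600 = 33.5%, against a true 30%.

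**Interim discontinuation when the true rate is 30%:**

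| Accrual (weeks) | C = 26, g = 0 | C = 26, g = 13 | C = 28, g = 0 | C = 28, g = 13 |
|---|---|---|---|---|
| 52 | 39.6% | 35.1% | 41.5% | 36.3% |
| 78 | 35.2% | 33.1% | 36.1% | 33.8% |
| 104 | 33.5% | 32.3% | 34.1% | 32.7% |
| 130 | 32.7% | 31.8% | 33.1% | 32.1% |

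With g = 28 every cell is 30.0%.

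**Dosed patients left out**, across p = 20% to 40%: with C = 26, 15.7% to 44.8% (g = 0) and 6.8% to 21.2% (g = 13); with C = 28, 16.6% to 47.9% and 7.8% to 24.2%.

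**AE withdrawal.** Assume a true 8% within the 30%, with the same hazard shape. The rate scales by 8/30: for example 39.6% × 8/30 = 10.6%. The interim shows 8.7% to 10.6% (g = 0) or 8.5% to 9.3% (g = 13), with C = 26. If half of AE withdrawals fall in the first 4 weeks, simulation gives 8.9% to 11.5% and 8.6% to 9.6%.

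**Certainty of direction.** The excess holds on average and needs at least one early stop among recent patients. In simulations of 760 patients with true rates of 20% and 30%, the interim proportion exceeded the final one in about 70% to 79% of runs with only 5 recent patients, and in at least 99% with 76 or more.

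**The case against.** The bias depends on two things the documents do not establish: that anyone was still on treatment on 30 Apr 2024, and that the SAP 5 and SAP 10 tables will be run on this set. Both conditions stand. The second, however, is open only because SAP 12 names no outputs.

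The size rests on assumed inputs. The 52-week case packs all accrual into the year before the cut-off, and nothing in the documents supports that in particular; the cited amendment is dated about 140 weeks before the cut-off, though this does not fix accrual. With 130 weeks of accrual and a 13-week gap the excess is 1.8 points; with a 24-week gap the rate is 30.3% to 30.8% (Week 26 reading). The range should be read with its low end in view.

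The Week 28 figures make completers wait for follow-up but admit drop-outs on the day they stop. If drop-outs also exit two weeks later, the ranges become 32.7% to 40.3% (no gap) and 32.0% to 35.8% (13-week gap): slightly lower, same conclusion. Protocol 6.4.1 treats anyone who leaves before all study visits are done as a premature discontinuation, which favours the Week 28 reading. SAP 12 does not say so.

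It is also fair that a descriptive interim in an unblinded, single-arm study without hypothesis tests may be judged not a major change. SAP 16 is then arguably not false, but protocol 9.5 still says there is no interim.

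Finally, restricting to finished patients is a common way to report complete records, no documented decision rests on the interim, and safety monitoring does not depend on it: protocol 6.4.2 provides that "On a quarterly basis during study conduct, all open-label safety data" are reviewed. This limits the consequence. It does not make the discontinuation percentage from such a set unbiased.

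**Conclusion.** The concern holds and should be fixed. The conflict between protocol 9.5 and SAP 12, the silence of SAP 16, and the missing purpose, outputs and completion rule need no assumption. The selection follows from the wording of SAP 12. Its effect is conditional on patients being on treatment at the cut-off and on the disposition and safety tables being run on the interim set.

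Under the stated assumptions the excess over a true 30% runs from about 2 points (130 weeks of accrual, 13-week gap) to about 10 points (52 weeks, no gap) on the Week 26 reading. It falls towards zero as the gap nears 26 weeks, and is zero on either reading at 28 weeks.

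Only the interim is affected. The final analysis uses all dosed patients, there is no hypothesis test and so no error rate to protect, and events in ongoing patients are still reported and enter the final tables.

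**What to change.** In SAP 12, define the interim set by first-dose date: every patient whose first open-label dose was at least 28 weeks before 30 Apr 2024, whatever their status. Entry then no longer depends on outcome, under either reading of completion. Alternatively, include all dosed patients up to the cut-off, show the number ongoing, and estimate discontinuation with ongoing patients censored. In either case state the purpose and the tables to be produced, and define completion. Bring protocol 9.5 and SAP 12 into agreement, and list the interim in SAP 16 as descriptive with no effect on the final analysis.

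The cost is SAP wording and a different subset flag. The first-dose-date set is somewhat smaller than SAP 12's on the Week 26 reading. With 760 dosed and a true rate of 30%:

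- 130 weeks of accrual to the cut-off: 760 × 102/130 = 596 instead of 632.
- 130 weeks with a 13-week gap: 760 × 115/130 = 672 instead of 702.
- 52 weeks with no gap, the least favourable case: 760 × 24/52 = 351 instead of 440.

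The alternative loses no patients but includes some with partial follow-up. Merely labelling the present set and showing the number ongoing would disclose the problem but leave the biased percentage in the tables.

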13. SAMPLE SIZE CONSIDERATION

The sample size is not based on statistical power considerations, but is based on the number of patients who may be eligible based on participation in the lead-in studies. It is expected the majority of patients who safely complete the lead-in studies will participate in this 26-week openlabel safety study.

Confidential Page 29 of 40

14. STATISTICAL SOFTWARE

Statistical analyses of efficacy and safety parameters will be performed using version 9.4 (or newer) of SAS^{\circledR} .

Confidential Page 30 of 40

15. DATA HANDLING CONVENTIONS

15.1 Visit Time Windows

If more than one assessment is available in the same analysis window for MADRS or for CGI-S, the later/latest record will be selected and assigned to the derived visit.

Table 15-2 presents the visits assigned for AIMS, BARS, and SAS corresponding to the range of treatment days (window) during which an actual visit may have occurred.

Confidential Page 31 of 40

Table 15-3 presents the visits assigned for clinical laboratory and ECG assessments corresponding to the range of treatment days (window) during which an actual visit may have occurred.

[figure not shown]

Table 15-4 presents the visits assigned for vital sign assessments corresponding to the range of treatment days (window) during which an actual visit may have occurred.

Confidential Page 32 of 40

15.2 Repeated or Unscheduled Assessments of Safety Parameters

For visits with repeated or unscheduled assessments of laboratory parameters, the non-missing values of the scheduled assessment will be used for summary statistics. If the scheduled assessments are missing, the last value from repeated or unscheduled assessments within the analysis window will be used for the visit. If repeated or unscheduled AIMS, BARS, SAS, vital signs or ECGs occur, apply the time-window rule and select the last non-missing values for each visit or endpoint.

All assessments during the Open-label Treatment Period will be included in PCS value determination and will be presented in the data listings.

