7.8.3 Rescue Medications

Medications for the acute treatment of extrapyramidal symptoms and akathisia are allowed.

Zolpidem may be taken for insomnia, in the evening at bedtime and prior to midnight for the treatment of insomnia. If zolpidem is not available in specific regions, another sedative hypnotic may be approved by the Sponsor or designee.

The date of each dose of rescue medication administration as well as the name and dosage regimen of the rescue medication must be recorded on the eCRF.

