10.5.2 Barnes Akathisia Rating Scale (BARS)

Descriptive statistics for BARS total score at baseline and changes from baseline at each assessment visit (including the end of the Open-label Treatment Period) will be presented for the Safety Population.

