10.5.3 Simpson-Angus Rating Scale (SAS)

Descriptive statistics for SAS total score at baseline and changes from baseline at each assessment visit (including the end of the Open-label Treatment Period) will be presented for the Safety Population.

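### A symptomatic AIMS, BARS or SAS rating followed by a later rating in the same window can drop out of every scale table: add a worst-value summary and a count of EPS rescue use

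*SAP*

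**What the plan says.** SAP 15.2 has a separate rule for the EPS scales, vital signs and ECG. It begins "If repeated or unscheduled AIMS, BARS, SAS, vital signs or ECGs occur" and goes on to "apply the time-window rule and select the last non-missing values for each visit or endpoint". For laboratory parameters the same section puts the scheduled visit first: "the non-missing values of the scheduled assessment will be used for summary statistics". It then adds: "All assessments during the Open-label Treatment Period will be included in PCS value determination and will be presented in the data listings".

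The planned scale outputs are in SAP 10.5.1 to 10.5.3. For akathisia the plan is "Descriptive statistics for BARS total score at baseline and changes from baseline at each assessment visit". For parkinsonism it is "Descriptive statistics for SAS total score at baseline and changes from baseline at each assessment visit". AIMS is handled in the same way, and all three include the end of the Open-label Treatment Period. None of these sections plans a worst value, a shift table or a threshold count.

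On rescue treatment, Protocol 7.8.3 says "Medications for the acute treatment of extrapyramidal symptoms and akathisia are allowed" and requires recording: "The date of each dose of rescue medication administration as well as the name and dosage regimen of the rescue medication must be recorded". Protocol 8.4 permits unscheduled repeat assessments for safety reasons or at the investigator's discretion.

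**The concern.** Safety and tolerability are the primary objective, the study has no comparator arm, and the three scales are its structured measure of EPS. If a patient is rated while symptomatic, takes rescue medication and is rated again in the same window, the by-visit summary takes the later value. For laboratory values, vital signs and ECG, an extreme reading that is not selected can still count in a PCS table. The EPS scales have no equivalent, so a discarded high rating reaches no scale table. At stake is whether the report can show how high the ratings went in individual patients, and how many patients needed drug treatment for these symptoms.

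**Working it through.** The plan states no EPS rate, rescue rate or standard deviation, so there is no figure to reproduce. The check has three parts.

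**1. When the rule acts.** Table 1-1 schedules the scales after baseline on Days 8, 29, 57, 85, 113, 141, 169 and 183. The gaps are 21, 28, 28, 28, 28, 28 and 14 days, with one scheduled rating per visit. The last-value rule changes a result only if an extra rating falls in the same window. Such ratings are allowed but not required, either before or after rescue. The window limits of Table 15-2 could not be read in the text available, so window widths were not checked.

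**2. Which output holds the symptomatic rating.** Take a patient with a baseline score of 0 and a symptomatic score of 4 (an assumed value on the 0 to 9 BARS total) who is back at 0 on rescue:

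| Ratings in the window | Last value (SAP 15.2) | Scheduled value first | Worst value |
|---|---|---|---|
| Unscheduled 4, then scheduled 0 on rescue | 0 | 0 | 4 |
| Scheduled 4, then unscheduled 0 on rescue | 0 | 4 | 4 |
| Scheduled 0, then unscheduled 4 with new symptoms | 4 | 0 | 4 |
| One scheduled rating of 0, on rescue | 0 | 0 | 0 |

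The by-visit result depends on the order of the ratings under either selection rule. The worst value does not. In the last row no symptomatic rating was made, so only a count of rescue use shows the episode.

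PCS criteria are given in SAP Tables 10-2 (laboratory), 10-4 (vital signs) and 10-5 (ECG). None covers AIMS, BARS or SAS. In the first two rows of the table, therefore, the score of 4 appears only in the listings.

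**3. Effect on a visit mean.** Let f be the share of patients with two ratings in one window, d the points between the two ratings, and q the share of those pairs in which the later rating is the lower one. Choosing the last rather than the first rating changes a falling pair by -d and a rising pair by +d, so

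shift = f × [-d × q + d × (1 - q)] = -f × d × (2q - 1).

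The documents give none of f, d or q. The assumed ranges are f from 0.5% to 5% and d from 2 to 4 points. With about 760 patients, f corresponds to 0.005 × 760 = 3.8 up to 0.05 × 760 = 38 patients.

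- q = 1 (every later rating lower): -0.005 × 2 = -0.01, to -0.05 × 4 = -0.20 points.
- q = 0.5: 0.
- q = 0 (every later rating higher): +0.01 to +0.20 points.

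Neither the size nor the sign follows from the documents.

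**The case against.** The strongest reply is that the effect is conditional and EPS is reported elsewhere. Adverse events are asked about at every visit. SAP 10.1 tabulates EPS events by preferred term under narrow and broad queries. It also tabulates all treatment-emergent events by severity, using the most severe occurrence. SAP 8.3 tabulates concomitant drugs by therapeutic class and preferred term. All ratings are listed, and the scale analyses follow Protocol 9.4.5.5, which asked only for descriptive change.

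Much of this stands, and it limits the gap to the scale tables. It does not close it. Protocol 8.2.1.4 elicits adverse events with a non-leading question, so the event tables complement the structured ratings without replacing them. A drug table shows which drugs were taken but not which were given for EPS. Listings for about 760 patients give no frequency.

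Three stronger readings are tempting and are not supported:

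- A reader might infer that the rule biases the scale results toward no change. The third row of the table shows it can equally select the symptomatic rating. A scheduled rating made on rescue shows treated status under any selection rule.
- A reader might infer that the laboratory rule, scheduled value first, is the cure. It gives the same treated value in the first row and discards the symptomatic rating in the third.
- A reader might add that ratings 21 to 28 days apart between Day 8 and Day 169 miss treated episodes. That concerns assessment frequency. No choice among recorded values recovers an episode that was never rated.

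**Conclusion.** The point holds as a reporting gap in a primary-objective safety outcome. Under the current SAP a symptomatic AIMS, BARS or SAS rating can be left out of every scale table when a later rating falls in the same window, because no scale output uses all ratings. How often this would happen is unknown. It needs two ratings in one window, and the documents neither require nor predict that. The range of -0.20 to +0.20 points for a visit-mean BARS rests entirely on assumed f, d and q and is not an estimate. The documents do not show that EPS will be understated overall. The change is still worth making: it costs little, uses data already recorded, and gives a result that does not depend on the order of the ratings.

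**What to change.** Keep the by-visit selection rule in SAP 15.2 as it is, and make three additions.

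1. In SAP 10.5.1 to 10.5.3, for AIMS, BARS and SAS, summarise each patient's worst (highest) post-baseline value and the change from baseline to it. Use all on-treatment ratings, scheduled and unscheduled. Restrict these to the open-label period, because baseline is set before the double-blind treatment of the lead-in study.
2. In SAP 15.2, state that all ratings in the Open-label Treatment Period enter this summary, in parallel with the existing provision for PCS values.
3. In SAP 10.5, give the number and percentage of patients who started a medication for EPS or akathisia on or after the first open-label dose, from the rescue-medication eCRF data. Protocol 7.8.3 also covers sleep medication and does not list the reason for use among the recorded items, so the SAP should say how the EPS and akathisia entries will be identified.

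The cost is SAP wording and a few table rows, with no new procedure or data collection. The downside is that the EPS figures may look slightly less favourable.
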